#### 5.3.2 ITT analysis

- Primary approach: The undetermined SVR will be treated as SVR failure.
- Secondary approach: Any imputation will be not be made to the participants who did not initiate or died during the treatment period. For the other participants, we will use the imputed SVR that was generated for the mITT sample above.

#### 5.3.3 Per-protocol analysis

The missing SVR will be excluded by the definition of per-protocol sample. Therefore, the analysis will use completely observed SVR, successful or failed, for this analysis without necessity of imputation.

#### 5.4 Statistical Model

Multivariable logistic regression will be applied to test the overall effectiveness of DOT or PN on the SVR (success vs. failure) as the primary outcome. The arm indicator will serve as the primary predictor. The CONSORT and ICH-9 statistical analysis guidelines suggest that, any baseline characteristics, even if significantly unbalanced between arms, should not be included in the multivariable logistic model since baseline imbalance could be due to chance rather than systematic bias in randomized studies but include as the covariates the randomization stratification variables. In the HERO study, they are: site/city, clinic type (OAT and CHC) and stage of liver disease (cirrhosis vs no).

The primary mITT sample, nonetheless, might no longer represent a randomized pool of participants since the characteristics of participants who initiated treatments may be unequal between the two models of care which may have differential effects on triggering treatment initiations due to difference in modalities of treatment initiation and delivery. Therefore, there could exist baseline characteristics that are unbalanced beyond chance among initiated participants between the two arms. We will declare imbalance if a baseline characteristic is significantly different between the two arms with a two-sided p-value < 0.01 considering the multiplicity of testing. As such, we will include unbalanced baseline characteristics for adjusting purposes in multivariable models in addition to the randomization stratification variables, resulting in the following model:

$$\text{Logit}(P(\text{SVR})) = b_0 + b_1 * \text{TRT} + b_2 * \text{Site1} + \dots + b_8 * \text{Site7} + b_9 * \text{Clinic\_Type} + b_{10} * \text{Cirrhosis}$$

+ Unbalanced Covariates

We will consider exploring other methods to adjust potential imbalance using propensity scores or inverse probability weighting.

For the analysis of the secondary ITT sample, we will only include the randomization stratification variables following the CONSORT and ICH-9 statistical analysis guidelines since the ITT samples are purely randomized participants, resulting in the following model:

$$\text{Logit}(P(\text{SVR})) = b_0 + b_1 * \text{TRT} + b_2 * \text{Site1} + \dots + b_8 * \text{Site7} + b_9 * \text{Clinic\_Type} + b_{10} * \text{Cirrhosis}$$

For the analysis of PP model the approach applied to the analysis of the mITT sample will be applied.

Review of the monthly enrollment reports during the conduct of the study, however, consistently revealed that few participants have cirrhosis to the extent that there are sites and clinics without any randomized participants with cirrhosis. This imbalance raises a concern with respect to the logistic model fitting which may not result in convergence in regression coefficient estimation algorithms due to a potentially ill-conditioned data matrix. If this occurs, we plan to

remove the cirrhosis term in the above model and fit the following model as the primary multivariable model that include only sites and clinic types for adjusting purpose.

$$\text{Logit}(P(\text{SVR})) = b_0 + b_1 * \text{TRT} + b_2 * \text{Site1} + \dots + b_8 * \text{Site7} + b_9 * \text{Clinic\_Type}$$

+ Unbalanced Covariates

We will report the adjusted odds-ratio (OR) with a 95% confidence interval (CI) for the estimate of the DOT vs. PN effect on SVR. We will also compute 95% CIs for the overall and arm-specific SVR rate using an exact (Clopper-Pearson) method to compare with results from other trials. Again, this analysis will be repeated for each of the three analytic samples albeit with different adjusting variables depending on the constituency of the samples: mITT, ITT and PP.

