## 11.4 Sample Size Determination

Sample size N=300 per arm, or a total of N=600, was determined based on feasibility of recruitment from all sites during the study period. Power analysis for each hypothesis below is conservatively conducted based on a reduced sample size (N= 270 per arm, or N=540 in total) after considering 10% attrition rates. The target power is 80% with a two-sided significance level of 0.05. To this end, minimally detectable effect sizes and widths of 95% confidence intervals were computed with those parameters and the sample size after attrition.

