### 3.3 Per protocol analytic sample

This per protocol (PP) analytic sample includes the enrolled study participants who 1) were randomized; 2) initiated treatment; 3) complied with the randomly assigned models of care without cross over any time during the 12-week treatment; and 4) had SVR outcome data (yes vs. no). This sample is referred to as the per-protocol (PP) analytic sample. The PP sample will be a subset of the mITT sample which is in turn a subset of the ITT sample.

The intention-to-treat principle reflects the principle that once the intervention was randomly assigned to a participant, the participant's intervention assignment will not change in the analysis even if s/he crossed over the other intervention during the trial period or did not complete intervention activities. The application of this ITT principle reflects the real-world goal of the HERO study which is to treat all PWID with HCV (i.e., all randomized individuals).

However, as the HERO study was designed as of a pragmatic randomized clinical trial (RCT), the ITT sample will not be used as the primary analytic sample because the outcomes are defined conditions on the initiation. Furthermore, the primary (SVR) and several of the other secondary outcomes (treatment completion, adherence) are only relevant among those who initiated treatment.

**All statistical analyses proposed in the present SAP will be repeated for each analytic sample.** Comparison across the three analytic samples will be compared to assess internal or external validities or limitations of the study findings. In particular, analysis of the secondary ITT sample will provide estimates of milestones along the HCV cascade of care by study arm and in the full sample. All statistical analyses will be conducted using SAS v9.4 and R 3.5 or higher, and a two-tailed significance level of 0.05 will be applied to all testing and confidence intervals.

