### 5.5 Power analysis

The HERO study was planned to recruit N=300 participants in each arm in the mITT sample. Considering the base 80% SVR rate in the PN arm, a minimum difference of 9% between the two arms will be detected (i.e., 89% vs. 80%, OR=2.1) with the planned sample size in a multivariable logistic regression model in which adjusting variables explain 10% of variation in the predictor variable. This study posits that a >9% difference in SVR between the PN and DOT groups will be clinically significant based on studies that showed that SVR in treatment naive patients was >90%.

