### 6.1 Subgroups to be compared

The primary subgroups and their levels are as follows:

- Demographic factors:
  - Sex: Males vs. Females
  - Age: <30 vs.  $\geq 30$
  - Race/Ethnicity: African American vs other; White vs. Other
  - Ethnicity: Latino (Yes vs. No)
  - Employment: Employed vs. Unemployed
  - Education:  $\leq$ HS diploma vs  $>$ HS diploma

- Married/Co-habitating vs. Other
- Housing: Unstable vs. stable
- Ability of transportation vs. Inability
- Clinical factors:
  - Opioid agonist treatment (OAT) clinic vs. community health clinic (CHC)
  - Any medication for OUD in the past 3 months: methadone/buprenorphine vs. none
  - HIV Co-Infection (yes vs. no)
  - HIV viral load: <200copies/mL vs. ≥200copies/mL
  - HCV Genotype (3 vs other)
  - HBV Co-infection: yes vs. no (+ vs. -)
  - Cirrhosis (yes vs. no)
  - Depression (severe/moderate vs. mild/none)
  - Anxiety (severe/moderate vs. mild/none)
  - HCV Treatment naïve vs. experienced
- Alcohol and Drug use:
  - Hazardous alcohol at baseline (yes vs. no)
  - Hazardous alcohol during treatment (yes vs. no)
  - Amphetamine at baseline (UTOX): Yes vs. No
  - Amphetamine during treatment (UTOX): Yes vs. No
  - Benzodiazepine at baseline (UTOX): Yes vs. No
  - Benzodiazepine during treatment (UTOX): Yes vs. No
  - Cocaine at baseline (UTOX): Yes vs. No
  - Cocaine during treatment (UTOX): Yes vs. No
  - THC/Cannabis at baseline (UTOX): Yes vs. No
  - THC/Cannabis during treatment (UTOX): Yes vs. No
  - Opiate at baseline (UTOX): Yes vs. No
  - Opiate during treatment (UTOX): Yes vs. No

- Oxycodone at baseline (UTOX): Yes vs. No
- Oxycodone during treatment (UTOX): Yes vs. No
- Any drug screen + at baseline (UTOX): Yes vs. No
- Any drug screen + during treatment (UTOX): Yes vs. No
- Injecting Behaviors:
  - Last drug injection at baseline: within 5-8 weeks vs 0-4 weeks
  - Last drug injection at baseline: within 9-12 weeks vs 0-4 weeks
  - Times IDU a day at baseline ( $\geq 2$  VS  $<2$ )
  - Times IDU a day during treatment ( $\geq 2$  VS  $<2$ )
  - Times IDU a day at baseline ( $\geq 3$  VS  $<3$ )
  - Times IDU a day during treatment ( $\geq 3$  VS  $<3$ )

Note: Additional subgroup analyses will be conducted based on investigator-driven proposals on concept sheets

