### 6.2.2 Assessment of heterogeneity of models care effect across subgroups

The following multivariable model will be used to both: 1) estimate and test DOT vs PN effects in each subgroup (i.e., DOT vs. PN in each of OAT and CHC); and 2) estimate test Subgroups effects in each of DOT and PN arms (OAT vs. CHC in each of DOT and PN arms).

$$\text{Logit}(P(\text{SVR})) = b_0 + b_1 * \text{Subgroup indicator} + b_2 * \text{TRT} + b_3 * \text{Subgroup indicator} * \text{TRT} + b_4 * \text{Site1} + \dots + b_{10} * \text{Site7}$$

The primary interest of this subgroup analysis will be estimating the DOT vs. PN effect on SVR in terms of point (i.e., odds-ratio) and interval estimates (i.e., 95%CI) and testing significance of DOT vs. PN effects in each group. The analysis results will also be graphically displayed in a forest plot. The secondary interest will be testing significance of the interaction term that represents a difference in DOT vs. PN effect on SVR between subgroups.

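### If the primary model does not converge, SAP 5.4 drops cirrhosis, which is not needed; the sparse-data problem lies mainly in the cirrhosis-by-arm subgroup model of 6.2.2, which has no fallback

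*SAP*

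**What the plan says.** Protocol 5.4 stratifies randomisation by city, clinic setting and cirrhosis. SAP 5.4 enters all three in the primary logistic model as main effects: arm, seven site indicators, clinic type and cirrhosis, plus any baseline covariates found unbalanced.

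The same section reports that "few participants have cirrhosis to the extent that there are sites and clinics without any randomized participants with cirrhosis". It fears that this could make the data matrix ill-conditioned and stop the fit converging. Only in that event will the analysts "remove the cirrhosis term in the above model and fit the following model as the primary multivariable model". The section does not say how non-convergence is to be recognised.

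SAP 6.1 lists cirrhosis among the primary subgroups. SAP 6.2.2 fits subgroup, arm, their interaction and site by logistic regression to "estimate and test DOT vs PN effects in each subgroup", with an odds ratio and 95% CI for each level. SAP section 6 names no method for sparse cells. Protocol 11.11 mentions exact logistic regression, but only for factors associated with resistance and reinfection.

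**The concern.** The safeguard is attached to the wrong model. A site without cirrhotic participants is a gap in a site-by-cirrhosis table, and the primary model has no site-by-cirrhosis term. If the rule fires, the primary analysis loses a factor that the trial randomised by, although the arm effect could have been estimated with that factor retained.

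The subgroup model does contain a term that sparse cirrhosis can break, the cirrhosis-by-arm interaction, and it has no fallback. What is at stake there is a listed subgroup result: an infinite or zero odds ratio with a meaningless Wald interval on the forest plot. The two independent statisticians would have no agreed way to handle it.

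**Working it through.** **Inputs.** SVR is 80% (PN) and 89% (DOT), with 300 per arm and adjusting variables explaining 10% of the variation in arm (SAP 5.5). The test is two-sided at 0.05 (SAP 3.3) with 80% power (Protocol 11.4). The planned cirrhosis share is 21% (Protocol 11.10), about 126 of 600. The actual count K is not given, so K is an assumption, split evenly with m = K/2 per arm.

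**The plan's own figure.** SAP 5.4 gives no number for convergence. The SVR rates come from 5.5, which states: "Considering the base 80% SVR rate in the PN arm, a minimum difference of 9% between the two arms will be detected". The effective size is 300 × (1 − 0.10) = 270 per arm. Solving the two-proportion formula for 80% power gives 8.7 points (8.9 on the Wald log-odds scale), and power for 89% vs 80% is 82.6%. The 9 points reproduce. The odds ratio is (0.89/0.11)/(0.80/0.20) = 2.02; the SAP's 2.1 corresponds to 89.4%.

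**Step 1: is the primary model singular?** In simulated trials (N = 600, 8 sites, cirrhotic participants confined to 3 or 5 sites), the design matrix always had full rank (11 of 11), with a condition number of about 11 to 14. Maximum likelihood never failed when cirrhotic participants had both outcomes. The simulations left out the unbalanced covariates, so this covers only the terms that the SAP names.

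**Step 2: when does the primary fit fail on cirrhosis?** Only when all cirrhotic participants share one result. The chance that all succeed is 0.80^m × 0.89^m:
- K = 12: 0.262 × 0.497 = 0.130
- K = 20: 0.107 × 0.312 = 0.033
- K = 30: 0.035 × 0.174 = 0.006

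The arm log odds ratio stayed finite in these trials. With and without cirrhosis, it differed by about 0.002 to 0.012 when the cirrhosis coefficient was infinite.

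**Step 3: what does dropping cirrhosis do to the arm effect?** With no cirrhosis effect, the average shift in the log odds ratio is about 0.002. With a cirrhosis odds ratio of 0.4 (assumed), it is 0.005 at K = 12, rising to 0.022 at K = 126. The standard error is about 0.24. Power changes by about 1 point or less.

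**Step 4: when does the subgroup model fail?** The odds ratio in the cirrhosis level is infinite, zero or indeterminate if all cirrhotic participants in either arm share an outcome. Ignoring the very small chance that all fail, with p the SVR rate in cirrhosis in each arm:

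P = 1 − (1 − p_PN^m)(1 − p_DOT^m)

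At K = 12 and 80%/89%: 1 − (1 − 0.262)(1 − 0.497) = 0.629.

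If cirrhosis has an odds ratio of 0.4 for SVR, the PN odds are 4 × 0.4 = 1.6 (61.5%) and the DOT odds 8.09 × 0.4 = 3.24 (76.4%). At K = 12: 1 − (1 − 0.054)(1 − 0.199) = 0.242.

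| SVR in cirrhosis (PN/DOT) | K = 12 | 20 | 30 | 60 | 126 |
|---|---|---|---|---|---|
| 80%/89% | 63% | 39% | 20% | 3% | 0.06% |
| 61.5%/76.4% (odds ratio 0.4) | 24% | 8% | 2% | <0.1% | ~0 |
| 80%/80% | 46% | 20% | 7% | 0.3% | ~0 |
| 95%/95% | 93% | 84% | 71% | 38% | 8% |

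The last row is an upper bound. It is relevant to the per-protocol sample, which excludes undetermined SVR instead of counting it as failure. Protocol 2.1 cites 95–96% for this regimen.

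**Step 5: does the alternative work?** Firth estimation converged in every simulated trial, for both the main-effects and the cirrhosis-by-arm model.

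**Step 6: the trigger.** In a further simulation at K = 12 and 80%/89%, a standard fit that stops on the relative change in deviance (1e-8) reported convergence in 179 of 179 separated trials, with a median absolute cirrhosis coefficient of about 14.5. A software convergence message alone is therefore not a reliable trigger.

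**The case against.** The strongest reply is that SAP 5.4 is an ordinary pre-specified convergence fallback. It is conditional, does not depend on the treatment effect, and barely changes the primary estimate. All of that stands. The convergence worry is also not baseless: with 12 cirrhotic participants at 80%/89%, the cirrhosis term separates in about 13% of trials, though by a different route from the one the SAP describes.

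The size of the subgroup problem depends on a count that the documents do not give and on SVR among cirrhotic participants. If cirrhosis lowers SVR materially, or the count is near the planned share, the problem is small. The SAP also lists other subgroups that might be sparse, such as HBV co-infection, but gives no counts for them.

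The proposed remedy has limits too. It is also triggered by the data, and it puts two estimators on one forest plot, whereas SAP 6.2 wants a consistent framework. With 6 to 10 cirrhotic participants per arm, a Firth odds ratio is finite but still imprecise. Showing counts only would be defensible, but the SAP does not provide for that either.

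A reader might infer that the SAP discards a stratification factor outright, or that the primary comparison is at risk. The documents support neither: removal happens only on non-convergence, and the arm estimate hardly moves.

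**Conclusion.** The point holds as a cheap improvement. Empty site or clinic cells do not make the stated primary model singular. Where the fit does fail on cirrhosis, the arm odds ratio remains finite, so removing the factor is unnecessary. The effect on the primary estimate is negligible (0.002 to 0.02 on the log odds scale).

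The material gap is the cirrhosis-by-arm model in 6.2.2. At the design SVR rates, its cirrhosis-level odds ratio has no usable value in about 63%, 39%, 20% and 3% of trials with 12, 20, 30 and 60 cirrhotic participants. With a cirrhosis odds ratio of 0.4, this falls to about 24%, 8% and 2% at 12, 20 and 30. At the planned 21% it is near zero at the design rates, and reaches about 8% only if SVR is 95% in both arms. It would go too far to say that the subgroup odds ratio is often undefined: that is true at about 20 or fewer cirrhotic participants at the design rates, and the SAP says only that there are few.

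**What to change.** In SAP 5.4, replace the removal rule. Keep site, clinic type and cirrhosis in the primary model. If separation or non-convergence is detected, refit the same model by Firth penalised likelihood with profile-likelihood CIs. Define the trigger by an explicit separation check, so that both statisticians reach the same model.

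In 6.2.1 and 6.2.2, use Firth with profile-likelihood CIs for any subgroup factor with an empty arm-by-level-by-SVR cell. Show the cell counts and mark those rows on the forest plot. Add a sentence on how penalised estimates will be pooled in the multiple-imputation analyses of 5.3.

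The cost is a few sentences of SAP text. The downside is slight shrinkage and a different estimator in the marked rows. The gain is almost entirely in the sparse subgroups.

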### 5.5 Power analysis

The HERO study was planned to recruit N=300 participants in each arm in the mITT sample. Considering the base 80% SVR rate in the PN arm, a minimum difference of 9% between the two arms will be detected (i.e., 89% vs. 80%, OR=2.1) with the planned sample size in a multivariable logistic regression model in which adjusting variables explain 10% of variation in the predictor variable. This study posits that a >9% difference in SVR between the PN and DOT groups will be clinically significant based on studies that showed that SVR in treatment naive patients was >90%.

## 6 Subgroup Analysis

Subgroup analysis will be conducted to assess potential heterogeneity of models of care effect across the levels of subgroups (section 6.1). The subgroup analysis will estimate and test: 1) main subgroup effect (section 6.2.1); and 2) the interaction between subgroup and the models of care to assess both between-arm and within-arm subgroup effects (section 6.2.2).

### 6.1 Subgroups to be compared

The primary subgroups and their levels are as follows:

- Demographic factors:
  - Sex: Males vs. Females
  - Age: <30 vs.  $\geq 30$
  - Race/Ethnicity: African American vs other; White vs. Other
  - Ethnicity: Latino (Yes vs. No)
  - Employment: Employed vs. Unemployed
  - Education:  $\leq$ HS diploma vs  $>$ HS diploma

- Married/Co-habitating vs. Other
- Housing: Unstable vs. stable
- Ability of transportation vs. Inability
- Clinical factors:
  - Opioid agonist treatment (OAT) clinic vs. community health clinic (CHC)
  - Any medication for OUD in the past 3 months: methadone/buprenorphine vs. none
  - HIV Co-Infection (yes vs. no)
  - HIV viral load: <200copies/mL vs. ≥200copies/mL
  - HCV Genotype (3 vs other)
  - HBV Co-infection: yes vs. no (+ vs. -)
  - Cirrhosis (yes vs. no)
  - Depression (severe/moderate vs. mild/none)
  - Anxiety (severe/moderate vs. mild/none)
  - HCV Treatment naïve vs. experienced
- Alcohol and Drug use:
  - Hazardous alcohol at baseline (yes vs. no)
  - Hazardous alcohol during treatment (yes vs. no)
  - Amphetamine at baseline (UTOX): Yes vs. No
  - Amphetamine during treatment (UTOX): Yes vs. No
  - Benzodiazepine at baseline (UTOX): Yes vs. No
  - Benzodiazepine during treatment (UTOX): Yes vs. No
  - Cocaine at baseline (UTOX): Yes vs. No
  - Cocaine during treatment (UTOX): Yes vs. No
  - THC/Cannabis at baseline (UTOX): Yes vs. No
  - THC/Cannabis during treatment (UTOX): Yes vs. No
  - Opiate at baseline (UTOX): Yes vs. No
  - Opiate during treatment (UTOX): Yes vs. No

- Oxycodone at baseline (UTOX): Yes vs. No
- Oxycodone during treatment (UTOX): Yes vs. No
- Any drug screen + at baseline (UTOX): Yes vs. No
- Any drug screen + during treatment (UTOX): Yes vs. No
- Injecting Behaviors:
  - Last drug injection at baseline: within 5-8 weeks vs 0-4 weeks
  - Last drug injection at baseline: within 9-12 weeks vs 0-4 weeks
  - Times IDU a day at baseline ( $\geq 2$  VS  $<2$ )
  - Times IDU a day during treatment ( $\geq 2$  VS  $<2$ )
  - Times IDU a day at baseline ( $\geq 3$  VS  $<3$ )
  - Times IDU a day during treatment ( $\geq 3$  VS  $<3$ )

Note: Additional subgroup analyses will be conducted based on investigator-driven proposals on concept sheets

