### Statistical Model

The precision of proportion of participants who develop resistance or reinfection will be determined with 95% confidence intervals (CIs) calculated using exact binomial methods. To identify factors associated with resistance or reinfection, we will conduct bivariate analysis using (exact) logistic regressions for both continuous and dummy-coded categorical variables. A series of bivariate analyses will be followed by a multivariable logistic regression that includes all factors significant in the bivariate analysis at a two-sided 0.05 significance level. All analyses will be separately conducted for each of resistance and reinfection outcomes. For the examination of association between resistance and adherence in particular, a multivariable logistic regression will also be applied in which overall adherence will be the primary predictor in the presence of other factors identified in the bivariate logistic regression analysis. In all multivariable analysis, the mDOT arm indicator will be included for adjusting purpose.

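### The SAP tests age, PHQ-9, GAD-7 and baseline injections per day against SVR only as two-level cuts, which gives up power if their effects are graded

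*SAP*

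**What the plan says.** SAP 6.1 lists the subgroups. Age is split at 30. PHQ-9 appears as "Depression (severe/moderate vs. mild/none", and GAD-7 is split in the same way. Injections per day at baseline is split once at 2 and again at 3. Time since last injection has three bands, entered as two contrasts with the most recent band; the first is "Last drug injection at baseline: within 5-8 weeks vs 0-4 weeks".

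SAP 6.2.1 fits SVR on one subgroup indicator, arm and site. SAP 6.2.2 adds the product of indicator and arm. SAP 6.2 says one common framework covers all subgroup analyses, so no other form of these factors is foreseen. SAP 6.2.2 gives first place to the DOT versus PN odds ratio within each level and second place to "testing significance of the interaction term that represents a difference in DOT vs. PN effect on SVR between subgroups".

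Table 1 of the SAP summarises age, PHQ-9, GAD-7 and injections per day as mean (SD). It shows time since last injection only in the three bands.

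The protocol is less restrictive. For resistance and reinfection, section 11.11 plans "bivariate analysis using (exact) logistic regressions for both continuous and dummy-coded categorical variables". For within-arm analyses, the power statement in 11.10 covers binary and continuous factors; the matching statement in SAP 6.3 mentions binary factors only.

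**The concern.** Secondary Objective 2 (Protocol 3.3) is to find factors associated with SVR and other key outcomes. It hypothesises that psychosocial factors, mental illness among them, go with lower SVR in one arm and not the other. Protocol 11.8 asks for formal interaction tests. If such a factor acts by degrees, an indicator treats everyone on one side of the cut as alike and discards part of the gradient.

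The loss grows as the split becomes uneven, and the age cut is likely to be uneven: the protocol expects a mean age of 43.9. Two cuts on injections per day give two overlapping tests of one variable, each at 0.05. At stake is the chance of seeing gradients in data the trial already holds. Neither document justifies restricting these tests to cuts.

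**Working it through.** **Inputs from the documents.** Significance: "a two-tailed significance level of 0.05 will be applied to all testing and confidence intervals" (SAP 3.3). Power: "The target power is 80% with a two-sided significance level of 0.05" (Protocol 11.4). Size: "The HERO study was planned to recruit N=300 participants in each arm in the mITT sample" (SAP 5.5), or the protocol's "reduced sample size (N= 270 per arm, or N=540 in total) after considering 10% attrition rates" (11.4). Base SVR is 80%, and adjusting variables explain 10% of the predictor's variation, so effective n = 0.9n.

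**Assumptions.** The documents do not give the SD of age, the shares on each side of the cuts, or the odds ratio (OR) per SD of any factor on SVR. Ranges are used.

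**Step 1: the plan's own figure.** Power = Φ([Δ√n − 1.96√(2p̄q̄)] / √(p₁q₁ + p₂q₂)). For 80% versus 89%, √(2 × 0.845 × 0.155) = 0.5118 and √(0.16 + 0.0979) = 0.5078.

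- 300 per arm, effective 270: (1.4789 − 1.0032)/0.5078 = 0.937, so power is 82.6%.
- 270 per arm, effective 243: (1.4030 − 1.0032)/0.5078 = 0.787, so power is 78.4%.

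The detectable differences are 8.75 and 9.2 points, so the stated 9 points reproduces. The 12-point subgroup figure at N=300 gives 81.5% power and also reproduces. Neither document gives a figure for the cost of cutting.

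**Step 2: what a cut leaves.** For a normal score with a linear effect on the log-odds, cut at share p, the relative efficiency is e = φ(z_p)²/[p(1−p)]. Power after the cut = Φ((1.96 + z_power)√e − 1.96). With 80% uncut power the bracket is 1.96 + 0.8416 = 2.8016. At 50/50, e = 0.1592/0.25 = 0.637 and 2.8016 × 0.798 − 1.96 = 0.276, which gives 61%.

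| Split | e | Power left from 80% | Points lost |
|---|---|---|---|
| 50/50 | 0.637 | 61% | 19 |
| 30/70 | 0.576 | 57% | 23 |
| 20/80 | 0.490 | 50% | 30 |
| 10/90 | 0.342 | 37% | 43 |
| 5/95 | 0.224 | 26% | 54 |

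Over the same range of splits, the loss is 13 to 28 points if uncut power is 40%, and 6 to 12 points if it is 20%.

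**Step 3: the age cut.** Share under 30 = Φ((30 − 43.9)/SD).

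| Assumed SD (years) | Share under 30 | Power left from 80% |
|---|---|---|
| 8 | 4.1% | 24% |
| 10 | 8.2% | 34% |
| 12 | 12.3% | 41% |
| 13 | 14.2% | 44% |

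A single normal curve ignores the spread of site means in Table 2 of the protocol, from 30.0 to 55.0. Averaging Φ((30 − site mean)/SD) over eight equal sites gives 9% under 30 for a within-site SD of 7 years and 16% for an SD of 12. The one site with mean 30.0 supplies 70% and 39% of them respectively. Because the models carry site terms, much of that contrast is absorbed. Simulating this set-up at N=600 with a main-effect OR of 1.45 per SD and within-site SDs of 7, 9 and 12, the continuous term has 71%, 78% and 85% power and the cut 23%, 37% and 54%. For a main effect of 1.2 per SD the age loss is only about 14 to 18 points.

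**Step 4: simulation of the SAP models.** N=600, eight sites, 80% SVR, normal score independent of site, 1,500 runs per setting.

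| Test | OR per SD | Uncut | Cut 50/50 | Cut 20/80 | Cut 10/90 |
|---|---|---|---|---|---|
| Main effect | 1.2 | 43% | 27% | 26% | 22% |
| Main effect | 1.35 | about 83% | 65% | 57% | 47% |
| Main effect | 1.5 | 98% | 88% | 82% | 71% |
| Interaction | 1.2 | about 15% | 12% | 10% | 7% |
| Interaction | 1.35 | about 31% | 22% | 18% | 12% |
| Interaction | 1.5 | about 49% | 34% | 29% | 19% |
| Interaction | 1.8 | about 80% | 62% | 53% | 34% |

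For interactions of OR 1.2 to 1.5 per SD the loss is about 4 to 29 points. With a skewed score and a main effect of 1.35 per SD, power falls from 76–77% to 54–55% at splits of 50/50 and 80/20.

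**Step 5: the reverse case.** If the true effect is a step exactly at the cut (OR 1.8 or 2.2, splits from 50/50 to 10/90), the two-level test beats the linear term by 11 to 36 points.

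**The case against.** The strongest defence is purpose. SAP 6.2.2 puts DOT versus PN estimates within levels first, and those need levels. The cuts are prespecified, and Table 1 already bands the PHQ-9 and GAD-7 scores. Protocol 11.8 also frames heterogeneity by strata. This stands as a reason to keep the cuts for estimation and display. It is no reason to rest the association and interaction tests on them as well.

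A second defence is that the size of the loss is assumed. That also stands: interactions weak enough to be missed either way lose little, and a step at the cut favours the SAP's test. The documents give no reason to expect a step at age 30 or at the chosen scores.

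A third is that SAP 6.1 allows further subgroup analyses through concept sheets. That permits a continuous analysis but does not prespecify one.

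Stronger readings that a reader might infer are not supported:

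- That every factor test in the trial uses cuts. Protocol 11.11 keeps continuous predictors for resistance and reinfection; the point concerns the SAP's SVR models.
- That time since last injection has been cut to two levels. It has three bands in two contrasts, and the SAP shows no finer value. What is missing is a test that uses the ordering, and a statement of where third-band participants go in each contrast.
- That a non-significant result will be reported as absence of heterogeneity. The SAP promises odds ratios with intervals and says nothing of the kind.

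**Conclusion.** The point holds for four variables: age, PHQ-9, GAD-7 and baseline injections per day. Their SVR association and interaction tests use only two-level indicators although the recorded values exist.

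The cost is conditional on a roughly linear effect, a roughly normal score and an uncut test with 80% power. On those terms a cut leaves about 61% at 50/50, 57% at 30/70 and 37% at 10/90. For age it leaves about 24% to 44%, given an assumed SD of 8 to 13 years. A reader might take a loss of some 20 to 50 points as a property of the plan. It is not: for interactions of OR 1.2 to 1.5 per SD at N=600 the loss is about 4 to 29 points, and for a step at the cut the sign reverses.

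This is a worthwhile refinement of secondary analyses. The primary SVR comparison is unaffected.

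**What to change.** In SAP 6.2.1 and 6.2.2, base the association and arm-by-factor tests for age, PHQ-9, GAD-7 and baseline injections per day on the continuous value: linear per SD, with a spline or quadratic check, adjusted for arm and site as now. Say that these are the tests to be reported for the four factors, so that no second set of p-values builds up.

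Keep the listed cuts for the within-level DOT versus PN estimates and the forest plots, with one cut for injections per day instead of two. For time since last injection, add a one-degree-of-freedom trend across the three bands, and state how each pairwise contrast treats participants in the remaining band.

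The cost is SAP wording, a few model terms, a linearity check and one extra per-SD estimate per factor. No new data are needed.
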